### **3. INVESTIGATIONAL PLAN**

#### **3.1 Overall Design and Plan of the Study**

Eligible patients will be enrolled and maintenance therapy on protocol no less than 60 days and must be initiated no more than 180 days post ASCT.

Patients will have standard restaging studies prior to initiation of therapy.

Standard post transplant therapy per institutional guidelines will be unaltered including prophylaxis therapy, vaccinations and restaging.

Patients who have completed ASCT and meet eligibility criteria will initiate maintenance therapy based on time on enrollment either in the phase dose escalation or expansion portion of trial.

Patients' clinical laboratory values and toxicity must be as specified below within 5 days before the first dose of study drug:

- Platelet count  $\geq 100,000/\text{mm}^3$
- Neutrophil count  $\geq 1000/\text{mm}^3$  (No growth factors within 5 days)
- Total bilirubin  $\leq 1.5 \times \text{ULN}$
- Alanine aminotransferase (ALT) and aspartate aminotransferase (AST)  $\leq 3 \times \text{ULN}$
- Creatinine  $< 2.5 \text{ mg/dL}$

Recovered (ie,  $\leq$  Grade 1 toxicity) from the reversible effects of autologous stem cell transplant.

Each cycle will be defined as a 28 day cycle. Drug holidays and break in therapy including those due to holidays, physician discretion and drug delivery are allowed as needed. Study drug will begin at Lenalidomide (10 mg/day); after three cycles , provided the ANC is  $\geq$  1000/ $\mu$ L, platelet count  $\geq$  100,000/ $\mu$ L, and all nonhematologic toxicity is  $\leq$  grade 1, then the dose may be increased to 15 mg/day at discretion of physician.

MLN 9708 will be dosed at 3 mg flat dose on days 1, 8, 15 administered orally.

Patients will be allowed to receive radiotherapy for palliation of symptoms during the course of maintenance therapy

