**SAE if deemed appropriate by the Principal Investigator or the IND Sponsor, MDACC IND Office.**

- All events occurring during the conduct of a protocol and meeting the definition of a SAE must be reported to the IRB in accordance with the timeframes and procedures outlined in “University of Texas M. D. Anderson Cancer Center Institutional Review Board
- **All life-threatening or fatal events**, that are unexpected, and related to the study drug, must have a written report submitted within **24 hours**
- **Serious adverse events will be captured from the time the patient therapy and until 30 days after therapy discontinues. Serious adverse events must be followed until clinical recovery is complete and laboratory tests have returned to baseline, progression of the event has stabilized, or there has been acceptable resolution of the event.**
- **Additionally, any serious adverse events that occur after the 30 day time period that are related to the study treatment must be reported to MDACC IND Office. This may include the development of a secondary malignancy.**

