### **Reporting to FDA:**

- Serious adverse events will be forwarded to FDA by the IND Sponsor (Safety Project Manager MDACC IND Office) according to 21 CFR 312.32.

**It is the responsibility of the PI and the research team to ensure serious adverse events are reported according to the Code of Federal Regulations, Good Clinical Practices, the protocol guidelines, the sponsor's guidelines, and Institutional Review Board policy.**

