### **Reporting to Millennium:**

This is an investigator-initiated study. The principal investigator (who may also sometimes be referred to as the sponsor-investigator), is conducting the study and acting as the sponsor. Therefore, the legal/ethical obligations of the principal investigator include both those of a sponsor and those of an investigator.

**Sponsor-investigator must report all SAEs, regardless of expectedness or relationship with any study drug, to Millennium Pharmacovigilance (or designee) as soon as**

**possible, but no later than 5 calendar days of the sponsor-investigator's observation or awareness of the event. In the event that this is a multisite study, the sponsor-investigator is responsible to ensure that the SAE reports are sent to Millennium Pharmacovigilance (or designee) from all sites participating in the study. Subinvestigators must report all SAEs to the sponsor-investigator so that the sponsor-investigator can meet his/her foregoing reporting obligations to Millennium Pharmacovigilance, unless otherwise agreed between the sponsor-investigator and subinvestigator(s). Millennium Pharmacovigilance (or designee) may request follow-up information to a reported SAE, which the sponsor-investigator will be responsible for providing to Millennium Pharmacovigilance (or designee).**

**The SAE report must include event term(s), serious criteria, and the investigator's or sub-investigator's determination of both the intensity of the event(s) and the relationship of the event(s) to study drug administration.**

**Intensity for each SAE, including any lab abnormality, will be determined by using the NCI CTCAE, version used at your institution, as a guideline, whenever possible. The criteria are available online at <http://ctep.cancer.gov/reporting/ctc.html>.**

**Relationship to all study drugs for each SAE will be determined by the investigator or sub-investigator by responding yes or no to the question: Is there a reasonable possibility that the AE is associated with the study drug(s)?**

**Sponsor-investigator must also provide Millennium Pharmacovigilance with a copy of all communications with applicable regulatory authorities related to the study or study drug(s), including, but not limited to, telephone conversation logs, as soon as possible but no later than 5 calendar days of such communication.**

SAE and Pregnancy Reporting Contact Information
[contact]
Email: [contact]

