### Analysis plan, Sample Size and Power

The primary endpoint is PFS, defined as the time from autologous stem cell transplantation (ASCT) to the time of clinical progression, death, whichever occurs first or the time of last contact. It is hypothesized that the combination will prolong PFS compared to the current standard regimen. A total of 48 patients (dosed at 3 mg of Ixazomib) will be enrolled at an accrual rate of 2 patients per month over 24 months. Additional 48 months of follow-up is planned after the last patient is recruited into the trial. Assuming that PFS time follows an exponential distribution, and patients treated with the current standard regimens had a median PFS of 40 months, we will monitor the PFS using the method of Thall et al. (Thall, 2005). Let  $T_s$  and  $T_e$  represent the time to progression for the standard regimens and the proposed treatment regimen, respectively. We assume  $T_s|M_s$  and  $T_e|M_e$  follow an exponential distribution with respective median  $M_s$  and  $M_e$ . Furthermore, we assume that the prior for  $M_s$  follows an inverse gamma distribution  $IG(100, 3960)$  to reflect our knowledge of PFS for the patients treated with the standard regimens. This has a mean of 40 months, and a variance of 16.3. The prior for  $M_e$  is assumed to be  $IG(3, 80)$ , which has the same mean of 40 months and a larger variance of 1600 to reflect the uncertainty about the median PFS of the proposed treatment regimen.

The PFS will be monitored every six months, and the study will be terminated early if there is little evidence based on the available data that the median PFS of the patients treated with the proposed treatment regimen is 12 months or more than that of the patients treated with the standard regimens. The formal stopping rule is

$$\Pr(M_e > M_s + 12 \mid \text{data}) < 0.035$$

Specifically, the trial will be stopped early if there is less than 3.5% chance that the median PFS for the patients treated with the proposed treatment regimen is 12 months or more than the median PFS for the patients treated with the standard regimens. The probability cutoff 0.035 was chosen to obtain an early stopping probability around 10% (0.091) if the true median PFS for the proposed treatment regimen results in a 12 months improvement over the historical median PFS of 40 months.

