The operating characteristics of this decision rule are summarized in Table 1 using the onearmTTE software developed at the Department of Biostatistics at M.D. Anderson.

Table 1. Operating characteristics for the design (based on 2000 simulations)

True median Progression Free Survival (month)	Pr(stop early)	Average Number of Patients Treated (25th, 75th percentiles)
30	0.92	39.6 ( 32, 48 )

36	0.64	42.9 ( 42, 48 )
40	0.41	44.4 ( 48, 48 )
48	0.16	46.0 ( 48, 48 )
52	0.091	46.5 ( 48, 48 )
60	0.053	46.9 ( 48, 48 )

This monitoring will be carried out via the Clinical Trial Conduct (CTC) website (<https://biostatistics.mdanderson.org/ClinicalTrialConduct>) which is housed on a secure server at MDACC and maintained by the MDACC Department of Biostatistics. Access to the website will be gained through usernames and passwords provided by the MDACC Department of Biostatistics. Training on the use of the CTC will be provided by the biostatistical collaborator of the study, with emphasis on the importance of timely updating of follow-up times and recording of events. The monitoring rules for the PFS will be applied every six months with the probability criterion recomputed based on the most recent data available at that time. If the stopping rule is met, the study statistician, research nurse, and principal investigator will each receive an email notification that the stopping boundary has been met.

Because of the limited number of patients who have received the combination treatment, we will monitor the toxicity of the combination while we monitor the efficacy of it. Due to the lack of detailed information about the association between toxicity and efficacy, independency between the efficacy endpoints and toxicity endpoints is assumed, and the toxicity events are monitored continuously (Thall et al., 1996). The toxicity endpoint is defined as treatment-related unmanageable toxicities, including grade 3 non-hematologic effects, or grade 4 hematologic effects, that require delay or termination of the treatment during cycle 1. A toxicity rate of 30% or higher will not be considered acceptable. The prior probability of toxicity is assumed to follow a Beta (0.3, 0.7) distribution with one patient worth of information. The toxicity will be monitored by a cohort size of 4. At any time after at least 4 patients have completed toxicity evaluations, the trial will be stopped if the following statement is true

$$\Pr[\text{toxicity rate} > 30\% \mid \text{data}] > 0.95,$$

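### The study flow chart contradicts itself on the day 8 and day 15 checks that feed the cycle-1 toxicity stopping rule, and the last listed boundary (21/48) does not match the stated criterion

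*Combined protocol and SAP*

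**What the plan says.** **The stopping endpoint.** Section 5 (Analysis plan, Sample Size and Power) counts treatment-related unmanageable toxicities, including "grade 3 non-hematologic effects, or grade 4 hematologic effects, that require delay or termination of the treatment during cycle 1". A rate of 30% or more is unacceptable. "The prior probability of toxicity is assumed to follow a Beta (0.3, 0.7) distribution with one patient worth of information". Looks come after every 4 patients, and the trial stops when the posterior probability that the rate exceeds 30% is above 0.95. The listed boundaries run from 3/4 to 21/48.

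**The checks that supply the data.** In the Study Flow Chart (Section 8.1), the day 8 and day 15 columns sit under cycle 1, but their headers confine them to the dose-escalation phase. Footnote 7 of the same chart calls for the day 8 and day 15 assessments in cycle 1 and in any cycle in which the physician escalates. Section 3.1 assigns patients to a dose-escalation portion or an expansion portion according to when they enrol. Table 3-2 (Section 3.3.4) bases its within-cycle action on platelet and neutrophil counts on MLN9708 dosing days other than day 1.

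**After cycle 1.** After three cycles, if counts and toxicity allow, lenalidomide may go up: "then the dose may be increased to 15 mg/day at discretion of physician". Toxicity is evaluated before every cycle (Sections 3.3.3 and 3.10.3). On serious events, Section 4.1.1 says "All events occurring during the conduct of a protocol and meeting the definition of a SAE must be reported to the IRB"; "Serious adverse events will be forwarded to FDA by the IND Sponsor"; and the sponsor-investigator "must report all SAEs, regardless of expectedness or relationship with any study drug, to Millennium Pharmacovigilance". Section 7.2 adds safety updates and annual progress reports to the IRB.

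**The concern.** A stopping rule is only as good as the ascertainment of its endpoint. A grade 4 cytopenia that appears around day 8 or day 15 and recovers before the next cycle is seen only if someone draws blood then. Without that count, Table 3-2 is not triggered, no dose is withheld, and no event enters the tally. If some patients are checked in mid-cycle and others are not, the count mixes two levels of ascertainment, and the operating characteristics in Tables 2 and 3, which take every event as counted, no longer describe the rule in use. Establishing safety is part of the primary objective (Section 2.1), so this bears on patient protection and on the conclusion.

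Two smaller matters concern the same rule. The last listed boundary can be checked against the stated criterion. The rule also has no counterpart after cycle 1, which raises the question of whether later toxicity is covered at trial level.

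**Working it through.** **1. The schedule, passages side by side.**

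| Place | Who gets day 8 and day 15 checks in cycle 1 |
|---|---|
| Flow chart, column headers | Dose-escalation phase only |
| Flow chart, footnote 7 | Cycle 1, with no limit to a phase |
| Section 3.1 | Names both an escalation and an expansion portion, and sets no rule |
| Table 3-2 | Presupposes counts on dosing days after day 1 |

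The first two rows cannot both hold for an expansion patient. The dose-escalation phase cannot be resolved from the current text either: Section 3.1 gives one flat MLN9708 dose, and the only escalation it describes is the optional lenalidomide increase. In the text as extracted, the mark for footnote 7 stands on the physical-examination row. I read the footnote as covering all day 8 and day 15 assessments because it refers to assessments in general.

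Other text does not close the gap. The thrombocytopenia and neutropenia paragraphs of Section 3.4 refer back to the protocol's own schedule, with extra tests as clinical practice suggests. Take-home MLN9708 is supplied one cycle at a time (Storage, Handling, and Accountability), so dispensing creates no mid-cycle visit.

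**2. Reproducing Table 2.** Inputs, all from Section 5: prior Beta(0.3, 0.7), cohorts of 4, maximum 48, the listed boundaries. With x toxicities in n patients, the posterior is Beta(0.3 + x, 0.7 + n − x). Exact binomial recursion over cohorts gives:

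| True rate | Table 2 | Without the n = 48 look | With that look at 21 |
|---|---|---|---|
| 0.20 | 0.035 | 0.035 | 0.035 |
| 0.30 | 0.18 | 0.177 | 0.178 |
| 0.40 | 0.56 | 0.563 | 0.575 |
| 0.45 | 0.77 | 0.772 | 0.786 |
| 0.50 | 0.91 | 0.912 | 0.921 |

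Table 2 is therefore reproduced, and it leaves out the look at 48.

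**3. What under-counting would do.** The documents give no detection rate, so the missed share m is an assumption. The rule then sees the rate p × (1 − m), and Table 2 gives the stopping probability:

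- p = 0.40, m = 1/4: 0.40 × 0.75 = 0.30, so 0.56 becomes 0.18.
- p = 0.40, m = 1/2: 0.40 × 0.50 = 0.20, so 0.56 becomes 0.035.
- p = 0.50, m = 1/5: 0.50 × 0.80 = 0.40, so 0.91 becomes 0.56.
- m = 0: no change.

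**4. The boundary at 48.** Find the smallest x with Pr(rate > 0.30 | x, n) > 0.95. For n = 4 to 44 this returns 3, 5, 7, 9, 10, 12, 13, 15, 16, 18 and 19, exactly as listed. At n = 48, x = 19 gives 0.9147, x = 20 gives 0.9525 and x = 21 gives 0.9754. The criterion is met at 20. With the last look counted, moving from 21 to 20 raises the crossing probability from 0.178 to 0.186 at a true rate of 30%, and from 0.786 to 0.815 at 45%.

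**5. Later cycles.** The lenalidomide increase comes after three cycles, so no event that follows it can enter a cycle-1 count. If the same criterion were applied to the first cycle after escalation, with 12, 24 or 48 escalated patients (assumed numbers), it would cross with probability 0.120, 0.144 or 0.186 at a 30% rate.

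**The case against.** The best defence is that footnote 7 is the specific instruction, that it plainly requires the checks in cycle 1, and that the header looks like a remnant of an earlier phase. A site that follows the footnote loses nothing, and a careful clinician would draw counts anyway. Part of this stands: the documents do not show that any patient went unchecked. Non-haematologic events can come to light through patient report, and a cytopenia that persists would appear in the counts required before the next cycle. Only transient mid-cycle events are exposed. Still, the chart is what a site works from, and it gives two answers.

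On the boundary, one patient at full enrolment cannot shorten accrual. That is correct, and it is why this is only a consistency error.

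A reader might infer more from the cycle-1 window: that toxicity from cycle 2 onward is unmonitored at trial level, or that a later-cycle stopping boundary is required. The documents do not support this. Evaluation continues before each cycle, with dose-modification rules (Sections 3.3.3 to 3.3.5). Serious events go to the IRB, the FDA and the manufacturer. Section 4.1.1 lets the principal investigator or the IND Office report any important medical event as serious. Safety updates and annual reports give the IRB an aggregate view. Deaths count in the PFS futility rule, since PFS runs "to the time of clinical progression, death, whichever occurs first or the time of last contact". Nothing in Section 5 promises a later boundary, and no later-cycle rate for this combination is given. A cycle-1 window is a defensible design choice.

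**Conclusion.** The flow chart is wrong as written: its headers and its footnote 7 give incompatible rules for the mid-cycle checks in cycle 1, and these checks help detect grade 4 haematologic stopping events and supply the counts on which Table 3-2 acts. The size of any under-count cannot be derived from the documents. It ranges from nothing, if every patient is checked, to a large loss of stopping probability under the assumed missed shares above. Those figures treat missed events as occurring at random across patients.

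The listed 21/48 disagrees with the stated criterion, which 20/48 already meets at 0.9525. Table 2 does not change, because it excludes that look.

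That no pre-specified rate prompts trial-level action after cycle 1 is a fact about the design, not an error and not evidence of excess toxicity. It supports no more than an optional suggestion.

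**What to change.** **Reconcile the schedule.** Make the flow-chart headers, footnote 7 and Section 3.1 agree, so that one stated schedule of day 8 and day 15 assessments applies to every patient counted in the toxicity rule. Define the dose-escalation phase or remove the term. Which schedule to adopt is for the sponsor; none is proposed here. If patients have already been treated under the present text, report how many in the toxicity count had the mid-cycle assessments. The cost is a wording change in one table and one paragraph, plus that count.

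**Correct the boundary.** Either list 20/48 or restate the criterion so that 21/48 follows from it. This changes one number; Table 2 stands.

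**Optional, lower priority.** The sponsor may consider a pre-specified aggregate review of toxicity from cycle 2 onward, including after lenalidomide escalation, or one sentence saying that this is left by intent to the existing reporting. A tally limited to the first escalated cycle has clear limits. It is weak near 30%, it leaves out cycles 2 and 3 and patients who never escalate, and the 30% limit would need confirming because Section 3.1 selects escalated patients for tolerance. It would also require attributing treatment delays to toxicity. Section 4.1 ensures a record of laboratory values that cause a delay, but other events are captured only when the treating physician judges them clinically relevant, so this work is not free.

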which means that the trial will be stopped for toxicity if the posterior probability of the toxicity rate being greater than 30% is greater 95%. The early stopping boundaries for toxicity, shown in the format of

(The number of patients with toxicities) / (The number of patients treated),  
are  $\geq 3/4$ ,  $5/8$ ,  $7/12$ ,  $9/16$ ,  $10/20$ ,  $12/24$ ,  $13/28$ ,  $15/32$ ,  $16/36$ ,  $18/40$ ,  $19/44$ , and  $21/48$ .

Table 2. Operating characteristics for the stopping rules  
For excessive toxicity monitoring

True DLT Rate	Probability Stop Early	Mean sample size
0.20	0.035	46.5
0.30	0.18	41.8
0.40	0.56	30.7
0.45	0.77	23.8
0.50	0.91	17.8

Early termination of the trial can be caused by either lack of efficacy or excessive toxicity. If the efficacy and toxicity are considered jointly, the early stopping probabilities as shown in Table 3 will be higher than the probabilities shown in Tables 1 to 2.

Table 3: Operating characteristics considering efficacy and toxicity jointly

True median	True toxicity rate	Probability Stop Early
36	0.2	0.65
36	0.3	0.70
36	0.5	0.97
52	0.2	0.12
52	0.3	0.25
52	0.5	0.92
60	0.2	0.086
60	0.3	0.22
60	0.5	0.91

Patients' demographic and clinical characteristics at baseline will be summarized using descriptive statistics such as frequency distribution, mean ( $\pm$  s.d.) and median (range) accompanied by graphical analysis. Student t-test/Wilcoxon test and ANOVA/Kruskal-Wallis test will be used to compare continuous variables between different patient groups. The chi-square test or the Fisher's exact test will be applied to assess the association between two categorical variables (Woolson, 2002).

The response rates and incidence of new primary malignancy will be estimated along with 95% confidence intervals. Time-to-event outcomes, including PFS and overall survival (OS), will be estimated using the Kaplan-Meier method (Kaplan, 1958). log-rank test will be performed to test the difference in time-to-event distributions between patient groups (Mantel, 1966). Cox proportional hazards model will be used to include multiple covariates in the time-to-event analysis (Cox, 1972).

Toxicity data will be summarized by frequency tables. For the toxicity endpoint, per-treated analysis will be used to include any patient who received the treatment regardless of the eligibility nor the duration or dose of the treatment received.

The MDASI –myeloma symptom evaluation will be analyzed with descriptive analysis.

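### The last printed toxicity stopping boundary, 21/48, does not follow from the stated rule, which is already met at 20/48

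*Combined protocol and SAP*

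**What the plan says.** The toxicity monitoring is described in Section 5 of the combined protocol and SAP, under Analysis plan, Sample Size and Power. The elements that matter here are these.

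- Reference rate: "A toxicity rate of 30% or higher will not be considered acceptable".
- Prior: "The prior probability of toxicity is assumed to follow a Beta (0.3, 0.7) distribution with one patient worth of information".
- Spacing of looks: "The toxicity will be monitored by a cohort size of 4".
- When the rule applies: "At any time after at least 4 patients have completed toxicity evaluations, the trial will be stopped if the following statement is true". The statement is that the posterior probability of a toxicity rate above 30% exceeds 0.95.
- The same rule in words: "the trial will be stopped for toxicity if the posterior probability of the toxicity rate being greater than 30% is greater 95" per cent.
- Boundaries (toxicities/patients): 3/4, 5/8, 7/12, 9/16, 10/20, 12/24, 13/28, 15/32, 16/36, 18/40, 19/44 and 21/48.
- Endpoint window: related toxicities "that require delay or termination of the treatment during cycle 1".
- Planned size: "A total of 48 patients (dosed at 3 mg of Ixazomib) will be enrolled".

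Table 2 then gives the probability of stopping early and the mean sample size at true rates of 20%, 30%, 40%, 45% and 50%.

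**The concern.** The boundary list should follow from the prior, the 30% reference and the 0.95 cutoff, all of which are stated. Its last entry does not. With exactly 20 toxicities among 48 patients, the formula says stop and the list says the boundary has not been reached. The two would be used by different people: staff following the trial are likely to read the list, while anyone recomputing the criterion will use the formula. The printed entry is also the more lenient of the two.

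A second, lesser ambiguity sits beside it. The rule is worded to apply at any point from 4 patients on and a boundary is printed for 48, yet the text does not say whether 48 patients counts as a stopping look.

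What is at stake is whether the regimen is reported as having crossed its own toxicity limit, and whether the trial is formally stopped, in one borderline outcome.

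**Working it through.** **Posterior.** With x toxicities in n patients and a Beta(0.3, 0.7) prior, the toxicity rate has a Beta(0.3 + x, 0.7 + n − x) posterior. The boundary at each n is the smallest x for which Pr(rate > 0.30) > 0.95.

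**Boundaries.**

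| n | Printed | Smallest qualifying x | Posterior probability at that x |
|---|---|---|---|
| 4 | 3 | 3 | 0.9533 |
| 8 | 5 | 5 | 0.9628 |
| 12 | 7 | 7 | 0.9739 |
| 16 | 9 | 9 | 0.9821 |
| 20 | 10 | 10 | 0.9641 |
| 24 | 12 | 12 | 0.9764 |
| 28 | 13 | 13 | 0.9616 |
| 32 | 15 | 15 | 0.9744 |
| 36 | 16 | 16 | 0.9622 |
| 40 | 18 | 18 | 0.9744 |
| 44 | 19 | 19 | 0.9642 |
| 48 | **21** | **20** | 0.9525 |

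Eleven of the 12 entries reproduce, so this reading of the prior, reference and cutoff agrees with the rest of the list. At n = 48 the posterior is Beta(0.3 + x, 48.7 − x):

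- x = 19, Beta(19.3, 29.7): 0.9147, not met
- x = 20, Beta(20.3, 28.7): 0.9525, met
- x = 21, Beta(21.3, 27.7): 0.9754, met

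Rounding does not explain the difference. The printed 3/4 is accepted at 0.9533, a margin hardly larger than that of 20/48.

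**Table 2.** I computed the stopping probability exactly by binomial recursion in cohorts of 4, first with looks at 4 to 44 only, then adding a look at 48.

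| True rate | Table 2: stop; mean N | Looks 4–44: stop; mean N | Adding 48 with 21: stop | Adding 48 with 20: stop |
|---|---|---|---|---|
| 0.20 | 0.035; 46.5 | 0.035; 46.5 | 0.035 | 0.035 |
| 0.30 | 0.18; 41.8 | 0.176; 41.8 | 0.178 | 0.186 |
| 0.40 | 0.56; 30.7 | 0.563; 30.7 | 0.575 | 0.607 |
| 0.45 | 0.77; 23.8 | 0.772; 23.8 | 0.786 | 0.815 |
| 0.50 | 0.91; 17.8 | 0.912; 17.8 | 0.921 | 0.938 |

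Table 2 matches throughout only when the look at 48 is left out. Mean sample size is the same in all three versions, because a stop at 48 saves no patients.

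**Size of the disagreement.** Rule and list differ only when the count is exactly 20/48 and none of the 11 earlier boundaries was crossed. That probability is the difference between the last two columns, for example 0.607 − 0.575 = 0.032 at a true rate of 40%. It is 0.8% at 30%, 2.1% at 35%, 3.2% at 40% and 3.0% at 45%.

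**Possible origins of 21.** These are assumptions; the documents state none of them. A fixed 30% with a cutoff between about 0.9525 and 0.9533 gives the full printed list. So does replacing the fixed 30% by a random comparator rate of suitable precision: 20/48 then gives 0.9446 with Beta(150, 350) and 0.9485 with Beta(300, 700), both below 0.95. With Beta(600, 1400) it gives 0.9505 and with Beta(3000, 7000) 0.9521, and the boundary returns to 20.

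**The case against.** The case for leaving this alone is that the last boundary hardly operates. By 48 evaluable patients the planned 3 mg enrolment is complete, so no one is spared exposure through slower accrual. The endpoint looks at cycle 1 only, so every patient has passed the monitored period. The list is headed as early stopping boundaries, and stopping at the planned maximum is not early in that sense. Table 2 follows this convention, which largely answers whether 48 is a look. The random-comparator explanation depends on choosing a suitable precision and cannot be confirmed from the documents.

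Most of this stands, and it is why the point is small. It does not remove the contradiction. The written rule stops the trial, not merely accrual; it is not limited to fewer than 48 patients; and a boundary for 48 is printed. If that look does not act, the text should say so. If it does, the number must agree with the rule. The comparator is useful only as a possible origin for the sponsor to check.

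**Conclusion.** The discrepancy is real and exact: under the stated Beta(0.3, 0.7) prior, fixed 30% reference and 0.95 cutoff, the boundary at 48 patients is 20, and the printed 21 is one event too lenient. It affects one outcome, with probability at most about 3% at the true rates examined. It does not limit enrolment or change mean sample size, and no figure in Table 2 depends on it. The probabilities assume monitoring in complete cohorts of 4, as the plan describes, with independent patients and a constant toxicity rate. The documents do not show whether the list or the written rule is the one that departs from the sponsor's intention. A safety threshold that contradicts its own formula should still be corrected, in proportion to its small effect.

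**What to change.** Reconcile the list with the rule in Section 5. If the rule stands as written, the last entry becomes 20/48. If 21/48 came from another calculation, such as a random comparator rate or a slightly higher cutoff, state that calculation and correct the written rule instead.

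Add one sentence saying whether 48 patients is a stopping look. If it is not, say that the last entry is for reporting only, or remove it.

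The cost is one number, or a corrected statement of the rule, plus that sentence. No table needs rerunning if the look at 48 stays excluded. If it is to count, Table 2 changes as shown in the last two columns of the working, and Table 3, which combines the efficacy and toxicity rules, must be updated with it.
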